5.6 Data Analysis

- **Provide sample size determination and analysis (include anticipated rate of screen failures, study discontinuations, lost to follow-up etc.).**

In a recent EPIC study, the minimal clinically important difference for the four EPIC domains was defined as the difference in scores between patients who were completely satisfied with their symptom burden (function and bother combined) versus only somewhat satisfied. Minimally important differences ranged from 0.33 standard deviation (SD) to 0.5 SD, which translated into a difference of six points for urinary incontinence scores, four points for bowel, 10 points for sexual function, and 4 points for hormonal symptoms. In the proposed study, we consider these differences as the clinically meaningful between-group mean difference in symptom reduction. To detect a 0.33 SD difference in symptom reduction between patients receiving the automated PC symptom support versus standard information at 12

month with 90% power, we will need 394 participants (197 per group), based on using a regression analysis adjusting for baseline values (analysis of covariance) with an α of 0.0125 with 0.5 as an assumed correlation between baseline and follow-up symptom scores. Note that the α value was chosen conservatively to detect symptom reduction in any of the four domains. The power will be higher to detect a larger than 0.33 SD between-group difference in symptom reduction and also to detect the same difference with higher correlation than 0.5 between baseline and follow-up symptom values. Assuming conservatively 15% attrition at each assessment time, we propose to enroll 550 participants in total with an anticipated 397 participants to complete assessments at the second assessment time. The number of eligible prostate cancer patients at each site is sufficient for recruitment. For interval scale outcomes measures such as confidence in symptom self-management, the proposed sample size should give adequate power to detect at least 0.33 SD differences between groups.

- **Describe how, where and by whom the data will be analyzed.**

All data will be analyzed at the Ann Arbor VA. The qualitative data analyst, [name], the data manager, [name], and Drs. [name], [name] and [name] will participate in the data analysis.

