Aim 1 initial analyses and data verification: Analyses will be done in three phases. Baseline analysis (data verification) will include examining the distribution of all study variables to assess extreme values, missing data, variances, skewness, and type of distribution. Descriptive statistics will be used to describe the distribution of baseline variables in the two groups. We will use means, medians, and ranges for continuous variables such as age and baseline symptom scores, and we will use proportions for discrete variables. Baseline comparability of the two groups will be assessed using two-group t-tests for continuous variables, and chi-square tests for dichotomous or categorical variables. Variables found to be associated with the study groups will be included in subsequent analyses as covariates to adjust for potential differences between groups, and the results will be interpreted with any baseline imbalances in mind. We also will evaluate bivariate associations between patients' experimental condition and the outcomes, as well as between each covariate and the outcomes and between each covariate and group assignment. These analyses will be done to determine unadjusted measures of effect, assess possible confounders, and anticipate any collinearity in subsequent analyses. We will also report by study group the percent of patients who reached EPIC symptom scores above 70 (i.e., "better symptom burden") at both 5- and 12- months. In the final phase we will use multivariable models to estimate the intervention effect. We will conduct graphical analysis to explore variation in outcome variables over time and between the two experimental groups. We will evaluate the trends in symptom burden, knowledge and information need over time in the two study groups separately. Results of these graphical analyses will be used to fine-tune the analytic course described below.

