Aim 1 outcome analyses: Our primary outcomes for Aim 1 will be changes in symptom burden and bother scores at 5-months relative to baseline, using the EPIC measure. We will also evaluate these outcomes at the 12-month assessment point, but focus on the 5-month for primary outcome assessment as it is closest to the completion of the intervention. Multiple regression analysis will be used to evaluate the primary outcomes. The model will include an indicator for intervention group as the primary independent variable, and treatment type indicator (surgery vs. radiotherapy) and study site indicators as covariates. Baseline variables found to differ between the two study groups in the baseline analysis will also be included as covariates, though we expect the groups to be balanced on demographic and symptom scores by the randomization process. The coefficient for the intervention group indicator will be used to evaluate the impact of the personalized automated prostate cancer symptom management program compared to standard information. For change in symptom burden, we will repeat the analysis using each of the four symptom domains for EPIC. We will use the same analytic approach to evaluate changes in confidence in symptom self-management, our second Aim 1 outcome. We hypothesize that for both Aim 1 outcomes, intervention group survivors will have better scores at both 5- and 12-month assessments relative to those in the group (i.e., less symptom burden and better PC-QOL, more confidence in symptom self-management). For patients with available data at both 5- and 12-months, we will assess the trajectory of symptoms over time. This will be done using a linear mixed-effects model with random effects for each subject, an indicator for intervention group, an indicator of follow-up wave (5 versus 12 months) and an interaction of time by intervention group to model potential changes in the intervention effect on symptoms soon (at 5-months) vs. long (at 12-months) after the intervention is discontinued. If the interaction is not significant, we will drop the interaction term from the model and estimate the time-averaged difference in outcomes between the two study groups. Analyses of other outcomes, such as self-management implementation and confidence, will be done similarly.

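### Further Aim 1 covariates are chosen by significance tests between the randomised arms, so chance rather than prognosis completes the primary model; a fixed covariate list would cost only wording

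*Combined protocol and SAP*

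**What the plan says.** Section 5.6 (Data Analysis) gives the rule twice.

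- Under the initial Aim 1 analyses: "Baseline comparability of the two groups will be assessed using two-group t-tests for continuous variables, and chi-square tests for dichotomous or categorical variables". The consequence follows: "Variables found to be associated with the study groups will be included in subsequent analyses as covariates to adjust for potential differences between groups".
- Under the Aim 1 outcome analyses, for the primary regression: "Baseline variables found to differ between the two study groups in the baseline analysis will also be included as covariates". The same sentence says that balance is expected from randomisation.

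The covariates fixed for that regression are "treatment type indicator (surgery vs. radiotherapy) and study site indicators as covariates". No significance level for the baseline tests and no list of candidate variables is given. The approach is extended to confidence in self-management and to the other Aim 1 outcomes.

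The primary time point is 5 months: "Our primary outcomes for Aim 1 will be changes in symptom burden and bother scores at 5-months relative to baseline". The sample size is instead set at 12 months, for an analysis of covariance on the baseline value, "with an α of 0.0125 with 0.5 as an assumed correlation between baseline and follow-up symptom scores".

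For Aim 2, the same section names age, race/ethnicity, education and income as covariates in advance. Aim 1 has no comparable list, although Section 4.0 shows that age, ethnicity, relationship status, initial diagnosis date, service branch and PEPPI score are held for each participant.

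**The concern.** If allocation is sound, a baseline difference among all randomised participants is a chance event. Its p-value carries no information on whether the variable predicts EPIC. Selecting on that p-value admits irrelevant variables that happen to differ and excludes useful predictors that happen to be balanced. A covariate earns its place in a randomised comparison by predicting the outcome, and the plan has no rule that admits a variable for that reason.

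The rule also leaves the primary model open until arm labels have been used. With neither a threshold nor a candidate list, two analysts could follow the plan faithfully and fit different primary models. At stake are the prespecification of the main Aim 1 analysis and some precision that data already held could supply.

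**Working it through.** **1. The plan's own figure.** Inputs from Section 5.6: difference 0.33 SD, α 0.0125, power 90%, correlation 0.5. Sidedness is not stated; two-sided is assumed.

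n per arm = 2(1 − 0.5²)(2.498 + 1.282)² / 0.33² = 196.7, so 197 per arm and 394 in total, as stated. A one-sided α gives 171 per arm (342) and does not match. Completers after 15% loss at each assessment: 550 × 0.85 = 467.5 at 5 months and 550 × 0.85² = 397.4 at 12 months; the plan gives 397 for the latter.

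**2. How often chance adds a covariate.** Assumptions: k independent candidates, each tested at 5%. The chance that at least one enters is 1 − 0.95^k.

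| k | at least one enters |
|---|---|
| 6 (the non-fixed items in Section 4.0) | 26% |
| 10 | 40% |
| 15 | 54% |
| 20 | 64% |

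At a 10% level the values for 10, 15 and 20 candidates are 65%, 79% and 88%. Any one predictor stays out 95% of the time at the 5% level and 90% at the 10% level.

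**3. Size of the two-step test.** Let one covariate explain a share R² of residual variance, and let z_x be its standardised imbalance. Under the null the unadjusted statistic is √R²·z_x + √(1 − R²)·e and the adjusted statistic is e, with e standard normal and independent of z_x. The rule uses e when |z_x| > 1.96 and the unadjusted statistic otherwise. The true size at nominal 0.0125 is:

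| R² | size |
|---|---|
| 0.05 | 0.0120 |
| 0.10 | 0.0115 |
| 0.30 | 0.0092 |

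The test is conservative because, when the covariate is balanced, the unadjusted difference varies less than its standard error allows.

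**4. Power available from prespecified covariates.** Baseline EPIC is taken as in the model at correlation 0.5, as the sample size assumes. Power = Φ(0.33 / √(4 × 0.75 × (1 − R²) / N) − 2.498), where R² is the further share of residual variance explained.

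| Time point | N | R² = 0 | R² = 0.05 | R² = 0.10 |
|---|---|---|---|---|
| 5 months (primary) | 467.5 | 94.8% | 95.8% | 96.7% |
| 12 months | 397 | 90.3% | 91.9% | 93.4% |

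The gain is 1.0 to 1.9 points at 5 months and 1.6 to 3.1 points at 12 months. In completers, N × R²/(1 − R²) at 12 months is 397 × 0.05/0.95 = 21 to 397 × 0.10/0.90 = 44.

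**The case against.** The strongest reply is that little is lost. Site and treatment type are fixed. On the plan's attrition figures the primary 5-month analysis already exceeds its 90% target if baseline EPIC is in the model, and the extra covariates add only 1 to 2 points. No figure in the documents shows that age or time since treatment predicts EPIC once baseline EPIC is included, so the 5-10% is an assumption. So are the number of candidates, their independence and the 5% level. All of this stands, and it limits the size of the point.

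Two further replies stand in part. Baseline comparison is placed in the first phase of the analysis and the rule uses baseline variables only, so the rule itself does not select on outcomes. The same paragraph does let plots of outcomes by arm adjust the later analysis, but that is a separate source of freedom. Also, the plan does not say whether the baseline tests use all randomised participants or completers. Among completers, a difference could reflect differential dropout rather than chance alone.

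A reader might draw stronger conclusions that the documents do not support:

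- *Inflated false positives.* The rule by itself lowers the error rate slightly.
- *A model chosen after unblinding.* No analyst blinding is described, so there is none to break. What can be said is that the selection tests need the arm labels.
- *A loss of power from about 90% to 79%.* That gap arises only if baseline EPIC itself enters through this rule (simulated at 197 per arm, correlation 0.5: 78.7% against 89.4% when always adjusted). Whether baseline EPIC is in the model is a separate inconsistency: the sample-size paragraph assumes it and the outcome paragraph does not list it.
- *Strong predictors omitted.* The documents do not show that the remaining variables are strong predictors.

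**Conclusion.** The point holds as a defect of prespecification with a modest numerical cost. The selection rule is stated, not inferred, and it picks covariates on chance imbalance instead of prognosis. It leaves part of the primary Aim 1 model undetermined until data by arm are examined. The treatment estimate is not invalidated. The quantified cost is one or two points of power at 5 months, two or three at 12 months, and slight conservatism. These figures rest on the assumed 5% selection level, 6 to 20 independent candidates, a further R² of 5-10% for power (5-30% for size), two-sided α 0.0125, correlation 0.5 and baseline EPIC in the model. The change is worth making because it needs no new data and no new participants.

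**What to change.** In Section 5.6, delete both sentences that add covariates because the arms differ, and delete the between-arm baseline tests. Keep the descriptive baseline table by arm.

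In the paragraph on Aim 1 outcome analyses, name one covariate set before anyone looks at data by arm:

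- the baseline score of the outcome analysed: the same EPIC domain or, for confidence, its baseline value if collected;
- study site;
- treatment type;
- age;
- time since treatment or since diagnosis, whichever is held (Section 7.0 lists the former; Sections 4.0 and 5.1 list the diagnosis date).

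The baseline score must be on the list. Otherwise, removing the selection rule would also remove the only route by which that paragraph could admit it, and the model would not match the analysis of covariance behind the sample size.

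Use the same set at 5 and 12 months and for the other Aim 1 outcomes, each with its own baseline score where there is one. Present adjustment for any chance imbalance only as a sensitivity analysis.

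The cost is plan wording and a few degrees of freedom.

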5.4 Inclusion/Exclusion Criteria

- **Describe the criteria that determine who will be included in or excluded from the study.**

Veteran participants:

Participants will be selected from CDW who meet the following eligibility criteria:

- Veteran patient at one of the four study sites
- History of treatment for prostate cancer treated by surgery, radiation or androgen deprivation therapy between 1-10 years prior to identification
- Has phone number on file and ability to converse on the telephone in English
- No dementia or other significant mental impairment

A random sample of those identified will be asked to participate. Those who elect to participate, and who have a qualifying Brief Screener score (1 or higher on at least 1 symptom) will be randomized to the study. We estimate as many as 553 - 650 veterans will be randomized. All participants will be 40-80 years old at the time of identification, and all will be male as this is a study of prostate cancer; otherwise we expect the health status of these veterans to be varied.

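### The 394-completer calculation assumes adjustment for the baseline EPIC score, but the Aim 1 model includes that score only if the arms differ on it, and by-arm outcome graphs may refine the plan with no exemption for the primary model

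*Combined protocol and SAP*

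**What the plan says.** All three relevant texts are in section 5.6, Data Analysis.

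- **Sample size paragraph.** It asks for 394 participants (197 per group) for 90% power at 12 months to detect 0.33 SD in symptom reduction. The alpha is 0.0125, chosen because there are four EPIC domains, and the assumed correlation between baseline and follow-up is 0.5. The calculation is "based on using a regression analysis adjusting for baseline values (analysis of covariance").
- **Aim 1 outcome analyses.** The primary outcome is change in EPIC from baseline, with a "focus on the 5-month for primary outcome assessment"; the same outcomes are also evaluated at 12 months. The multiple regression has the arm indicator plus "treatment type indicator (surgery vs. radiotherapy) and study site indicators as covariates". Other baseline variables are added only if the baseline analysis finds that they differ between arms, "though we expect the groups to be balanced on demographic and symptom scores by the randomization process". The baseline EPIC score is not among the fixed terms.
- **Aim 1 initial analyses and data verification.** Before the multivariable models, the plan examines arm-outcome associations: "These analyses will be done to determine unadjusted measures of effect, assess possible confounders, and anticipate any collinearity in subsequent analyses". It then adds: "We will conduct graphical analysis to explore variation in outcome variables over time and between the two experimental groups". The closing sentence is "Results of these graphical analyses will be used to fine-tune the analytic course described below". The text directly below opens with the primary 5-month regression.

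**The concern.** The sample size rests on unconditional baseline adjustment, while the analysis text makes that adjustment conditional on an imbalance that randomisation is expected to prevent. If the analyst follows the analysis text, the variance of the arm comparison is larger than the one used to size the trial, and the stated power is not delivered. This holds whether or not anyone refines the analysis after seeing data.

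The second matter is separate. The plan supports two readings of the primary model, a change score without baseline and a baseline-adjusted model. It also lets graphs of outcomes by arm refine what follows, with no statement that the primary model is already fixed. A reader of the results could not tell whether the model was settled before or after the arms were compared.

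**Working it through.** **Inputs.** From the sample size paragraph: difference 0.33 SD, alpha 0.0125, correlation r = 0.5, 197 per group, 15% attrition at each assessment, 550 enrolled. From section 5.2: 553 to 650 randomised. My assumptions: two-sided tests (sidedness is not stated, but only two-sided reproduces 394; one-sided gives 342), equal SD at baseline and follow-up, and the same alpha, difference and r at 5 months, where the plan states none.

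**Step 1: reproduce the plan's figure.** The residual SD under analysis of covariance is √(1 − r²) = √0.75 = 0.866. Then n per group = 2 × 0.75 × (2.498 + 1.282)² / 0.33² = 196.7, so 197 per group and 394 in total, which matches. Attrition also matches: 550 × 0.85² = 397.

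**Step 2: the same calculation without the baseline score.** The SD of change is √(2(1 − r)) = 1.0 at r = 0.5. The variance is 1.0 / 0.75 = 1.33 times larger. Then n per group = 2 × 1 × (2.498 + 1.282)² / 0.33² = 262.3, so 263 per group, or 526 completers instead of 394.

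**Step 3: power at the planned sizes.** The change-score and covariance columns use a two-sided noncentral t. The conditional column is simulated, with the baseline score entered only when the arms differ on it at an assumed 0.05 level. Five-month completers are 550 × 0.85 = 467 (233 per group) or 650 × 0.85 = 552 (276 per group).

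| Setting, r = 0.5 | Per group | Change score, no baseline | Baseline only if imbalanced | Baseline always in |
|---|---|---|---|---|
| 12 months, the plan's 394 | 197 | 78% | 79% | 90% |
| 5 months, 550 enrolled | 233 | 85% | 87% | 95% |
| 5 months, 650 enrolled | 276 | 91% | 93% | 98% |

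With 650 enrolled, 12-month completers would be 650 × 0.85² = 470, about 234 per group. That is in effect the middle row: roughly 85 to 87% against 95%.

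**Step 4: sensitivity to r.** At 233 per group, change score against baseline always in: 77% v 92% at r = 0.4, 85% v 95% at 0.5, 93% v 97% at 0.6, 98% v 99% at 0.7. The change score reaches 90% at r of about 0.56 with 233 per group, and about 0.63 with 197.

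**Step 5: an illustration of a choice made after seeing the arms.** Under the null, the two models' test statistics correlate √((1 + r)/2) = 0.866 at r = 0.5. If the more favourable were always kept, the chance that either exceeds 2.498 in absolute value is 1.94% per domain, against 1.25%. The conditional rule, whose baseline tests do not use outcomes, gives about 1.0%.

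**The case against.** Several points on the other side stand.

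- **Time point.** The 90% is stated for 12 months. A reader might infer that 5-month power falls below a stated target, but the documents give no 5-month target. The shortfall against a stated figure is the 12-month one.
- **Enrolment range.** With 650 enrolled, 5-month power is above 90% even without the baseline score.
- **Effect size and correlation.** The plan's important differences run from 0.33 to 0.5 SD. At 233 per group and r = 0.5, the change score has about 96% power at 0.4 SD and 99.8% at 0.5 SD. A correlation somewhat above 0.5 also closes the gap. Still, 0.33 SD and 0.5 are the values the plan chose to size the trial.
- **The analysis text is a rule, not a free choice.** Read literally, baseline enters if imbalanced, and that rule does not inflate error. It also does not restore the power: 79% at 197 per group.
- **The graph sentence.** Its reference to change over time suits the mixed model of trajectories, and the Aim 1 text does fix the endpoint, time point, method and core covariates.

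A reader might also infer that the plan lets the analyst pick a model by its p-value, with per-domain error near 1.9% and about 7.5% over four independent domains (1 − (1 − 0.0194)⁴). The documents do not support that. No text describes fitting both models and keeping the better one. The figure covers only two models, so it illustrates the risk without estimating or bounding it.

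**Conclusion.** The concern holds in two parts of unequal weight.

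The main one is a mismatch between the sample size basis and the analysis. The 394 is arithmetically correct, but only if the baseline score is always in the model. Under the Aim 1 text as written, 12-month power at the plan's own assumptions is about 78 to 79% instead of 90%. At 5 months it is about 85 to 87% with 550 enrolled and 91 to 93% with 650, against 95 to 98% with the baseline score always included. The 5-month figures assume that the 12-month alpha, difference and correlation carry over. The conditional figures also assume a 0.05 level for the baseline tests.

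The lesser one is that the sentence on graph-driven refinement does not exempt the primary model. The documents do not show that it was meant to reach that model, and no size can be put on its effect from the text. It is a gap in pre-specification, not a demonstrated inflation of error.

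The change should be made: it affects the primary analysis, supports the stated power and costs almost nothing.

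**What to change.** 1. In the Aim 1 outcome analyses, state that for each EPIC domain the regression at 5 and at 12 months always includes that domain's baseline score, with arm, treatment type and site. With baseline in the model, change and follow-up score give the same arm coefficient, so the change endpoint stays.
2. In the Aim 1 initial analyses, limit the refinement sentence to secondary or exploratory longitudinal analyses, and state that the primary model is fixed before outcomes are compared by arm.

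**Cost.** A few lines of text. The baseline score is already collected, and a change score cannot be computed without it, so no participant is lost. The 394 and the 550 do not change. The price is one degree of freedom per domain model and less freedom to adapt the primary model later.

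A separate point to raise on its own: the treatment indicator has two categories, while section 5.4 also admits androgen deprivation therapy ("History of treatment for prostate cancer treated by surgery, radiation or androgen deprivation therapy between 1-10 years prior to identification").

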There are three primary Veteran-reported trial outcomes which will be measured at 5- and 12-months post enrollment: 1) confidence in symptom self-management, 2) implementation of symptom self-management, and 3) symptom burden and PC-QOL. Self-efficacy in patient-physician interactions will also be assessed at baseline, 5-months and 12-months. Participants in the trial will be randomized by computer by VA Ann Arbor Healthcare System (VAAHS) study staff. We hypothesize better outcomes in the intervention arm relative to enhanced usual care. The impact of the intervention on two secondary psychosocial outcomes, overall subjective health and perceptions of cancer control, will be assessed only at the 12-month time point, when we believe the intervention is most likely to have had its impact on these outcomes. The trial will be conducted in four VA sites (Ann Arbor, Cleveland, Pittsburgh, and St. Louis) with a large and racial/ethnically diverse population of PC survivors between 1-10 years post-treatment. The intervention is based on a conceptual framework that describes how self-management contributes to positive outcomes for cancer patients and survivors; we also will utilize theoretical constructs from patient empowerment and cognitive behavioral therapy (CBT) to inform the content of our intervention. We will compare the quality of health care received in intervention and control subjects using guidelines for prostate cancer survivorship care developed by the Michigan Cancer Consortium as a benchmark. Finally, we will prepare for implementation of the intervention on a broader scale through a formative evaluation. This design will allow us to understand how the intervention can best optimize the quality of life and quality of care for Veterans with PC, and will inform how to implement the program more broadly with our primary care partners.

- **Include a description of how anticipated risk will be minimized and include an analysis of risk vs. potential benefit.**

How anticipated risk will be minimized:

Veteran participants:

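### Sample size and power are stated for the 12-month EPIC difference, but the analysis makes 5 months primary, and no testing order or alpha rule links the two times

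*Combined protocol and SAP*

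**What the plan says.** The sample-size paragraph of 5.6 Data Analysis defines the design difference at the later assessment: "To detect a 0.33 SD difference in symptom reduction between patients receiving the automated PC symptom support versus standard information at 12" months. It requires 394 participants, 197 per group, for 90% power. The method is a regression adjusted for baseline, "with an α of 0.0125 with 0.5 as an assumed correlation between baseline and follow-up symptom scores". That paragraph explains the alpha by the four EPIC domains and does not mention time points. It assumes 15% attrition at each assessment, 550 enrolled and 397 completing the second assessment.

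The Aim 1 outcome analyses in 5.6 name the change in EPIC scores from baseline to 5 months as the primary outcome. They add that 12 months will also be evaluated, with a "focus on the 5-month for primary outcome assessment as it is closest to the completion of the intervention". The same paragraph then hypothesises that "intervention group survivors will have better scores at both 5- and 12-month assessments". Its list of model covariates gives treatment type, study site and any imbalanced baseline variables. It does not expressly list the baseline EPIC score.

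Section 5.1 Study Design refers to "three primary Veteran-reported trial outcomes which will be measured at 5- and 12-months post enrollment": confidence in self-management, its implementation, and symptom burden with PC-QOL. The hypotheses in 3.0 Objectives also cover both times.

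**The concern.** The power statement and the primary analysis concern different assessments. A reader who takes the 90% as the power of the primary test is looking at the wrong time point, sample and expected retention.

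The status of the 12-month result is also open. The intervention calls run over 3 months (5.5 Study Evaluations), and the Aim 1 text plans a group-by-time interaction because the effect may change after the intervention stops. The two assessments could therefore differ. With both results in hand, the team could point to the Aim 1 analysis text to support a 5-month claim, or to the sizing paragraph and the hypotheses to support a 12-month claim. The level of 0.0125 is fully used by four domains at one time, so it would not cover a choice between the two.

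**Working it through.** **Inputs.** From the sample-size paragraph of 5.6: difference 0.33 SD, baseline to follow-up correlation 0.5, alpha 0.0125, power 90%, 550 enrolled, 15% attrition per assessment. Sidedness is not stated. Correlations between domains and between times are not given and are assumed below.

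**1. The plan's own figure.** With baseline adjustment the residual variance is 1 − 0.5² = 0.75. For a two-sided test, n per group = 2 × (2.498 + 1.282)² × 0.75 / 0.33² = 196.7, so 197, or 394 in total. This matches. A one-sided test would give 171 per group, so the plan's alpha is two-sided.

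**2. Which assessment the 397 belongs to.** 550 × 0.85 = 467.5 remain at 5 months and 550 × 0.85² = 397.4 at 12 months. The stated 397 is the 12-month number.

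**3. Power at each time**, for 0.33 SD at two-sided 0.0125. Power = Φ(0.33/s × √(N/4) − 2.498), where s is the residual SD. With baseline adjustment s = √0.75 = 0.866. For an unadjusted change score at correlation 0.5, s = √(2 × (1 − 0.5)) = 1.

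| | 5 months (N = 467.5) | 12 months (N = 397.4) |
|---|---|---|
| Baseline-adjusted | 94.8% | 90.3% |
| Unadjusted change score | 85.8% | 78.6% |

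Without baseline adjustment, 90% power would need 263 per group instead of 197.

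**4. What 0.0125 covers.** 4 × 0.0125 = 0.05, so four domains at one time use the whole level. Two times make eight tests. At 0.0125 each, the Bonferroni bound is 8 × 0.0125 = 0.10, and independent tests would give 1 − (1 − 0.0125)⁸ = 0.096.

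**5. Family-wise error if either time could count.** This was simulated from correlated normal test statistics under no effect.

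| Assumed domain correlation | Four tests, one time | Eight tests, time correlation 0.5 | Eight tests, time correlation 0.7 |
|---|---|---|---|
| 0 | 0.049 | 0.091 | 0.085 |
| 0.5 | 0.043 | 0.080 | 0.074 |
| 0.7 | 0.037 | 0.068 | 0.063 |

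Even at domain correlation 0.7 and time correlation 0.9 the eight-test figure is 0.053.

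**6. Cost of the alternative.** If either time were meant to support a primary claim, Bonferroni would use 0.05/8 = 0.00625 per test. Power would be 91.7% at 5 months and 85.6% at 12 months. Restoring 90% at 12 months would take 223 per group, 446 completers, and 446/0.85² = 617.3, so 618 enrolled.

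**The case against.** The strongest reply is that the Aim 1 analysis text settles the matter. It names 5 months as primary, gives a reason, and places 12 months second. The sizing paragraph contains no success criterion, the design section can be read as an assessment schedule, and expecting benefit at both times does not mean that either one suffices. Sizing on the later, smaller sample is also cautious for the earlier one.

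Much of this stands, and it rules out several stronger readings:

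- A reader might infer that no time point decides the trial. The documents do choose 5 months, in the section where that choice belongs. The fault is that the other sections were not brought into line with it.
- A reader might infer that the primary test is underpowered. It has more completers than the 394 required, if the sizing assumptions carry over to 5 months.
- A reader might infer that type I error is already inflated. That follows only if either time can support a primary claim, and no section says so.
- A reader might think of repeated looks at the data. No interim efficacy testing with stopping is described. The issue is tests at a second time point.
- A reader might expect the two times to disagree often. If the effect halved by 12 months they would give opposite results in a domain about 67–68% of the time, but the halving is an assumption without support in the documents. With a constant 0.33 SD the figure is 10–12%.

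The reply does not remove the mismatch between the sizing and analysis paragraphs, or the lack of any rule for a 12-month result. The hypothesis of benefit at both times stands in the same paragraph that makes 5 months primary.

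**Conclusion.** The inconsistency is real and should be corrected, although it does not threaten the sample size. The 90% power belongs to 12 months. The primary test at 5 months has about 95%, on condition that 0.33 SD and a correlation of 0.5 apply there too, which the documents do not say, and that baseline EPIC is in the model. If it is left out, an unadjusted change score has about 86% at 5 months and 79% at 12 months.

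With 5 months confirmed as the only primary time, 0.0125 per domain is sufficient. If either time may support a primary claim, family-wise error is about 0.06 to 0.09, for assumed domain correlations of 0 to 0.7 and time correlations of 0.5 to 0.7. The textual mismatch is certain; the error inflation is conditional on a rule that the plan neither states nor excludes.

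**What to change.** - In 5.1 and in both paragraphs of 5.6, state that the primary contrast is the four EPIC domain scores at 5 months, each tested at two-sided 0.0125.
- Make 12 months secondary. Test it in a domain at 0.0125 only if that domain's 5-month test is significant. Otherwise report the estimate with its confidence interval. Each domain then spends at most 0.0125, so the total stays at 0.05.
- Name the baseline EPIC domain score as a covariate in the Aim 1 model, to match the analysis of covariance used for sizing.
- Restate power as about 95% at 5 months (about 467 completers) and 90% at 12 months (397), and say that 0.33 SD and a correlation of 0.5 are assumed at both times.
- Label confidence in self-management and its implementation as secondary, or state the alpha that covers them, since 5.1 also calls them primary.

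This costs wording only, with no added participants or data. The one loss is that a 12-month effect without a 5-month effect in the same domain could not be claimed as confirmatory.
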